6.5.2. Discontinuation of a Study Site

The Sponsor may discontinue the study at a site for reasons that include GCP violations, protocol deviations, lack of enrollment or protection of the safety and wellbeing of a subject.

7. STUDY ASSESSMENTS AND PROCEDURES

7.1. Demography and Medical History

Subjects' demographic information will be collected and recorded. A complete systemic and ocular medical history will be taken at screening. Interim history will be taken at the remaining visits.

7.2. Efficacy Assessments

Note that these assessments are applied to the Study (or Operated) Eye Only.

- Slit Lamp Biomicroscopy examination including assessment of anterior chamber inflammation, including anterior chamber cell count (number of cells), which will be counted twice for each subject at each visit; and grading of anterior chamber flare on a 0-4 Scale
- Subject-Rated Ocular Pain Assessment (0-5 Scale)
- Use of Rescue therapy
- ETDRS Assessment of Best Corrected Visual Acuity by Pinhole Method

7.2.1. Procedures for Efficacy End-Point Assessments:

Subject-Rated Ocular Pain Assessment

Ocular pain is defined as throbbing, or aching, and is graded by subjects on a 5-point scale. On the assessment days, the subjects will be required to subjectively rate their pain in the study eye at the time of the visit. Each subject will be asked to subjectively rate their pain based on the scale as follows:

0 = None: Absence of pain.

1 = Minimal: Presence of minimal throbbing or aching pain (expected following cataract surgery)

2 = Mild: Presence of mild throbbing or aching pain, easily tolerated.

3 = Moderate: Presence of moderate throbbing or aching pain leading to the desire to use an analgesic.

4 = Severe: Presence of severe throbbing or aching pain that is not tolerable.

Anterior Chamber Cell Count and Grading of Anterior Chamber Flare

The biomicroscopy examination will be performed with the slit lamp using a slit-beam. The Investigator should use their usual examination technique. Anterior chamber cells should be counted twice using the high light intensity level and the high magnification (Haag-Streit 16

X or comparable), with the slit beam set at an oblique angle, and the height and width of the beam set to 1.0 X 1.0 mm.

1. Assessment of ACC will be performed by counting twice the number of cells seen in the field during the examination (see Section 7.3.3). There is no mandatory requirement of the minimum or maximum time interval between the two counts, but it is **recommended** that the two counts are performed within approximately 2 minutes of each other. Both counts will be recorded in the eCRF along with the time of each count. **Note: If >30 cells are observed, it will be recorded as >30 rather than obtaining the actual number of cells.**
2. Assessment of ACF will be assessed using the following Grading Scheme:

Grading Scheme – Anterior Chamber Flare

Grade	Description
0	None
1+	Faint
2+	Moderate (iris and lens details clear)
3+	Marked (iris and lens details hazy)
4+	Intense (fibrin or plastic aqueous)

7.3. Safety Assessments

Note that these assessments are applied to both eyes (at Screening, POD28/EOS (Part A) or POD22/EOS (Part B) or early termination) or just the Study (or Operated) eye as indicated in Table 2A or Table 2B (Schedule of Events).

Safety parameters include:

- Assessments of AEs
- ETDRS Assessment of Best Corrected Visual Acuity by Pinhole Method
- Slit Lamp Biomicroscopy including assessment of the following signs of inflammation: corneal edema, ciliary flush, bulbar conjunctival injection
- IOP Measurement
- Dilated Ophthalmoscopy

7.3.1. Assessment of Adverse Events

All AEs spontaneously reported by the subject and in response to an AE query from study personnel or revealed by observation, physical examination or other diagnostic procedures

will be recorded in the source document and on the appropriate pages of the eCRF. Any clinically relevant deterioration in a clinical finding is considered an AE and must be recorded. When possible, signs and symptoms indicating a common underlying pathology should be noted as one (1) comprehensive event. Any pre-existing medical condition that worsens after administration of study drug will also be considered as an AE.

Ocular complaints should not be addressed as AEs unless the complaint is outside the normal limits for cataract surgery or is associated with clinical sequelae (i.e., adverse slit lamp examination finding). Ocular complaints associated with and expected as a result of the surgery, that are not recorded as AEs in the eCRFs will be recorded as comments in the source documents.

See Section 8 for information on how to record AEs and how to capture relatedness to study procedures (including cataract surgery) or study drug.

7.3.2. ETDRS Best Corrected Visual Acuity Measurement by Pinhole Method

Best corrected visual acuity measurement will be performed using the ETDRS eye chart at a preferred (but not required) distance of 4 meters. The testing should be conducted under standardized lighting conditions using the pinhole method for all study visits except the day of surgery. Other testing distances may be used as long as it is consistent with the recommendations provided for the ETDRS chart being used and will be used at each visit consistently. The subject starts at the top of the chart and reads down until the subject reaches a row where the subject is unable to correctly read any letters on that line.

The ETDRS Acuity Log Score is calculated as follows:

1. Determine the last row where the subject can correctly identify at least one (1) letter in that row. This is the Base logMAR line.
2. Determine the log score for the Base logMAR line.
3. Add 0.02 (T=0.02) log units for every letter that is incorrectly identified up to and including the Base logMAR line.

The results will be recorded in the source documentation and the eCRF.

7.3.3. Slit Lamp Biomicrocopy

The number of anterior chamber cells will be counted twice and anterior chamber flare assessed as described in Section 7.2.1.

In addition to the assessment of the anterior chamber cells and flare, the following parameters will be evaluated using the following scales during the slit lamp exam:

Bulbar Conjunctival Injection

Grade	Description
0	Absent
1	Mild
2	Moderate
3	Severe

Sclera - Ciliary Flush

Grade	Description
0	Absent
1	Mild
2	Moderate
3	Severe

Corneal Edema

Grade	Description
0	Absent
1	Mild
2	Moderate
3	Severe

Lens Pathology (in the contralateral/non-surgical eye) will be evaluated as:

- Normal; no opacity in the lens
- Abnormal; existing opacity in the lens; aphakic or pseudophakic eyes or other abnormal findings.

7.3.4. IOP Measurement

IOP measurements will be performed utilizing Goldmann applanation tonometry according to the Investigator's standard procedure. All pressures will be recorded in mmHg. IOP

assessments will be performed at all study visits except the surgery visit as indicated in the Schedule of Events (Table 2A or Table 2B).

7.3.5. Dilated Ophthalmoscopy

A dilated fundus examination will be performed according to the Investigator's standard technique and will occur as indicated in the Schedule of Events (Table 2A or Table 2B). The Investigator should evaluate the vitreous, retina, macula, choroid, and optic nerve with cup/disc ratio and will note normal/abnormal findings.

The Investigator will determine whether or not abnormalities observed at the Screening visit would exclude a subject from study participation.

If a subject has a cataract in the non-operated eye at the Screening visit, the Investigator should make an assessment whether there has been a change in the size or composition of the cataract at the EOS/POD28 visit (Part A) or EOS/POD22 visit (Part B) or at early termination. This information will be recorded in the source document and eCRF.

8. ADVERSE EVENTS

8.1. Definition of Adverse Events (AEs)

Adverse event means any untoward medical occurrence in a subject or clinical investigation subject administered a pharmaceutical product and which does not necessarily have a causal relationship with this treatment (21CFR312.32 (a); ICF E6 Section 1). An AE can therefore be any unfavorable sign and unintended sign (including an abnormal laboratory finding), symptom, or disease temporally associated with the use of a medicinal (investigational) product, whether or not related to the medicinal (investigational) product.

Note:

- *Reporting of AEs that may or may not be related to the ocular surgical procedure depends on their severity:*
 - i. *An AE that the Investigator considers to be within what is normally expected for cataract surgery will be recorded in a table in the source documents and no further reporting is required.*
 - ii. *An AE that the Investigator considers to be outside what is normally expected for cataract surgery or is associated with clinical sequelae will be recorded in the full AE page in the source documents and also in the eCRF,*
- *Rescued subjects are considered to be treatment failures, and rescue itself is not considered an AE.*
- *Adverse events occurring in rescued subjects should be reported in the eCF.*
- *An anterior chamber cell count > 30 on POD1 that leads to disqualification of the subject prior to Randomization should be reported as an AE.*
- *An IOP > 30 mmHg after Randomization should be reported as an AE.*
- *An IOP ≥ 24 mmHg AND an IOP increase ≥ 10 mmHg from pre-dose baseline should be reported as an AE.*

The term “severe” is used to describe the intensity of an AE; the event itself could be of relatively minor clinical significance (e.g., ‘severe’ headache). This is not the same as “serious”. Seriousness of AEs is based on the outcome of an AE and usually associated with events that pose a threat to a subject’s life or functioning.

A Treatment Emergent Adverse Event (TEAE) will be defined as any AE that occurs after the study drug dosing is initiated. For the purpose of this study, a TEAE may be related to the ocular surgical procedure and/or to the initiation of the study drug.

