be considered in any persistent corneal ulceration while a subject is participating in this clinical trial.

In clinical studies evaluating the use of corticosteroids after ocular surgery, ocular adverse reactions that occurred in 5% to 15% of subjects included corneal edema, ciliary and conjunctival hyperemia, eye pain, photophobia, posterior capsule opacification, anterior chamber cells, anterior chamber flare, conjunctival edema, and blepharitis. Other ocular adverse reactions occurring in 1% to 5% of subjects included reduced visual acuity, punctate keratitis, eye inflammation, and iritis. Ocular adverse reactions occurring in less than 1% of subjects included application site discomfort or irritation, corneal pigmentation and striae, episcleritis, eye pruritus, eyelid irritation and crusting, foreign body sensation, increased lacrimation, macular edema, sclera hyperemia, and uveitis. Most of these reactions may have been the consequence of the surgical procedure.

Potential Risks Associated with the APP13007 Formulation

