10.3.3. Analysis of Safety

Analysis of safety data will be performed for all subjects in the Safety Population.

Adverse events (AE) will be summarized by total number of any AE, number of subjects reporting the AE, ocular AEs (affecting the study eye and/or the non-study eye and/or both eyes, when appropriate), ocular TEAEs in the study eye, systemic AEs, SAEs, suspected unexpected serious adverse reaction (SUSARs), discontinuing study drug due to an AE, by relationship to study drug and/or ocular surgical procedure, and by severity. Adverse events will be coded using Medical Dictionary for Regulatory Activities (MedDRA, most current version) and categorized by system organ class and preferred terms.

The analyses of IOP will include the summary statistics of IOP and its change from baseline (POD1/pre-dose) at each visit, the proportion of subjects with an IOP ≥ 24 mmHg AND an increase ≥ 10 mm Hg from pre-dose baseline, and the proportion of subjects with an IOP > 30 mmHg at any time following initiation of study drug.

The proportion of subjects with a visual acuity worsening from POD1/pre-dose visit of ≥ 2 lines will also be summarized.

Ocular symptoms, comfort grading assessment, ophthalmoscopy findings, and slit lamp biomicroscopy results will be categorically summarized.

Details of statistical analyses will be included in the SAP.

10.3.4. Interim Analysis:

No interim analyses are planned for this study.

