5.6.2. Adverse Events

Adverse events (AE) will be summarized by total number of any AE, number of subjects reporting the AE, ocular AEs (affecting the study eye and/or the non-study eye and/or both eyes, when appropriate), systemic AEs, SAEs, discontinuing study drug due to an AE, by relationship to study drug only, to ocular surgery only, or to both drug and ocular surgery, and by severity. Adverse events will be coded using Medical Dictionary for Regulatory Activities (MedDRA version 22.0 – March 2019) and categorized by system organ class and preferred terms.

See [Tables 14.3.1.1 – 14.3.1.3](#) for details.

All adverse events will be listed by both reported term and MedDRA term in [Listing 16.2.7.1](#) and [16.2.7.2](#).

	Document Number: CLN.001.SAP	Version: 0
	Document Title: Clinical Study CPN-201 Statistical Analysis Plan	Page 24 of 35

All serious and significant adverse events will be listed in [Table 14.3.2](#) and narrated in [Table 14.3.3](#).

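### AE tables will undercount non-serious ocular events judged expected after surgery, so four listed reactions with no scheduled assessment may go uncompared with vehicle

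*Protocol*

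**What the plan says.** The note in Protocol 8.1 opens by tying reporting to severity, but the rule that follows turns on expectedness. Under Note i, an event that the investigator finds normal for the surgery "will be recorded in a table in the source documents and no further reporting is required". Under Note ii, an event that is unusual for the surgery or "is associated with clinical sequelae will be recorded in the full AE page in the source documents and also in the eCRF". No term list, grade or time limit defines what counts as expected.

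Protocol 7.3.1 first sends all AEs to both source and eCRF, then makes an exception for expected ocular complaints: those "that are not recorded as AEs in the eCRFs will be recorded as comments in the source documents". The same section also says: "Any clinically relevant deterioration in a clinical finding is considered an AE and must be recorded".

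Protocol 1.4.1 lists ocular reactions seen in 5% to 15% of subjects in trials of corticosteroids after ocular surgery, and comments: "Most of these reactions may have been the consequence of the surgical procedure".

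SAP 5.6.2 breaks AEs down "by relationship to study drug only, to ocular surgery only, or to both drug and ocular surgery, and by severity". Protocol 10.3.3 also plans a summary of "ocular TEAEs in the study eye". The text of SAP 5.6.2 does not include it. SAP 6.6 (Changes to Protocol-Planned Analyses) declares one change only, the added analyses of anterior chamber cell grade, and the SAP Appendix does not mention the TEAE summary.

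**The concern.** Safety and tolerability against vehicle is the primary safety objective, and Protocol 1.4.2 states that this is the first use of APP13007 in humans. Many of the ocular reactions of interest look the same whether they come from the drug or from the operation. An investigator cannot separate the two in one patient; the comparison with vehicle can. Note i removes some of these events before that comparison is made, on an undefined judgement applied at about 8 centers.

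Two consequences follow for the SAP. The count of events related to surgery only comes from a database that excludes, by rule, the events most typical of surgery. And for a reaction that has no scheduled assessment, the AE record is the only route to a between-arm summary. AEs are also among the key data reviewed for progression from Part A to Part B (Protocol 3.3).

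**Working it through.** The plan gives no figure for AE capture, so there is none to reproduce. The check is a reading of the text, followed by an illustration.

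**1. Which events can be lost.** An event stays in source only if it is non-serious (Protocol 8.7.1 puts all SAEs in the eCRF), has no clinical sequelae (Note ii), is judged expected (Note i), and is not a clinically relevant deterioration in a finding (7.3.1). Raised IOP cannot be lost above the two thresholds in 8.1, where it must be reported as an AE. An AE around surgery that needs medication must also be entered (6.2.1).

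**2. Which listed reactions depend on an AE record.** Counting ciliary and conjunctival hyperemia separately, Protocol 1.4.1 names ten reactions in the 5% to 15% band.

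| Reaction | Scheduled assessment summarised by arm |
|---|---|
| Corneal edema, ciliary hyperemia, conjunctival hyperemia | Yes: graded signs, SAP 5.6.7 |
| Eye pain, anterior chamber cells, flare | Yes: efficacy endpoints, SAP 5.3 |
| Photophobia | None found |
| Blepharitis | None found |
| Conjunctival edema | No scale in Protocol 7.3.3 and no SAP summary |
| Posterior capsule opacification | Monitored at each visit under Protocol Table 3, but no SAP summary |

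Six are covered and four are not. On conjunctival edema, the slit-lamp footnotes to Protocol Tables 2A and 2B name it where Protocol 7.3.3 and the matching SAP footnotes name corneal edema. Even if the footnotes are read literally, no grade or table follows. Outside this list, IOP and visual acuity are also measured and compared (SAP 5.6.5, 5.6.6), and irritation is part of the ocular symptoms assessment that SAP 5.6.7 summarises.

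**3. Pre-dose events.** Day 0 AEs are recorded at POD1 (Protocol 6.2.1). Protocol 8.1 defines a TEAE as one occurring after dosing starts. SAP 5.1.6.1 completes partial dates so that AEs can be placed during study drug or not, but the text of SAP 5.6.2 states no rule that uses this. Tables 14.3.1.1 to 14.3.1.3 might; their shells are not visible.

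**4. Illustration of the undercount.** Inputs: n = 21 per arm (Protocol 10.4), and true incidence p between 5% and 15% (the band in Protocol 1.4.1). The share c of such events that reaches the eCRF is an assumption, varied from 1 to 0.25, because the documents give no value.

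P(at least one recorded case in an arm) = 1 − (1 − p·c)^21. For p = 15% and c = 0.5 this is 1 − 0.925^21 = 81%.

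| c | p = 15% | p = 10% | p = 5% |
|---|---|---|---|
| 1 | 97% | 89% | 66% |
| 0.75 | 92% | 81% | 55% |
| 0.5 | 81% | 66% | 41% |
| 0.25 | 55% | 41% | 23% |

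For a between-arm contrast of 15% and 5% with the same c in both arms, the risk ratio stays at 0.15c / 0.05c = 3.0. The risk difference shrinks from 10 points (c = 1) to 5 (c = 0.5) and 2.5 (c = 0.25). Power at two-sided 0.05 (normal approximation, pooled variance under the null) is 19%, 11% and 7%.

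**The case against.** The strongest reply is that the safety comparison does not rest on AE counts alone. A reader might infer that the primary safety comparison omits the ocular events the steroid class is known to cause. The documents do not support that. The anticipated class risks in Protocol 1.4.1 are raised IOP, cataract in the non-operated eye, delayed healing and infection. Raised IOP is a mandatory AE at two thresholds and is analysed by arm; lens findings in the non-study eye have their own table. The 5% to 15% list describes what was seen after surgery in steroid trials, which is not the same as what the steroid caused, and six of its ten terms are compared without the filter. This stands, and it confines the point to the AE tables and the four uncovered reactions.

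It is also fair to say that the exceptions are wide. Protocol 7.3.1 treats an adverse slit-lamp finding as a clinical sequela, so a site that reads the rule strictly may enter some cases of conjunctival edema or blepharitis. That limits the loss, but leaves it dependent on how each site reads the rule.

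A reader might also infer a bias between arms. Investigators are masked (Protocol 5.3), so similar filtering in both arms is the natural expectation. Events are still lost and the absolute difference still shrinks.

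Finally, a reader might infer that Day 0 events are mixed into the treatment columns. That cannot be shown without the table shells, and Protocol 10.3.3 itself also counts any AE. What can be shown is the missing study-eye TEAE summary and the absence of a stated rule.

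The illustration is open to criticism too: c is assumed, the at-least-one-case figure is not a between-arm measure, and power is only 19% with full capture. All p-values are descriptive. These points limit the weight of the numbers but do not remove the capture gap.

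**Conclusion.** The point holds in this limited form. Following the plan exactly keeps non-serious ocular AEs without sequelae that are judged expected after surgery out of the eCRF, so the AE tables, and the surgery-only count in particular, are incomplete by construction. Photophobia, blepharitis, conjunctival edema and posterior capsule opacification may not be compared between active and vehicle. IOP, visual acuity, corneal edema, ciliary flush, conjunctival injection, cells, flare, pain and irritation are covered by scheduled assessments.

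The size is unknown. The figures for 21 subjects per arm show how a given loss would act on a reaction at 5% to 15%. They rest on an assumed capture share, equal in both arms, and do not estimate what happened. Separately, SAP 5.6.2 departs from Protocol 10.3.3 on study-eye TEAEs without declaring it in SAP 6.6. In an exploratory study this does not undermine the design, but it is worth correcting because the remedy is cheap.

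**What to change.** - **Protocol 8.1 and 7.3.1:** enter in the eCRF the post-dose ocular events already held in source, with an 'expected for surgery: yes/no' flag. Reconcile the severity wording that introduces the note with the expectedness rule beneath it.
- **SAP 5.6.2, capture:** show the AE tables by arm with and without the flagged events.
- **SAP 5.6.2, timing:** restore the study-eye TEAE summary using the Protocol 8.1 definition, and list pre-dose events separately. If the summary is dropped on purpose, declare that in SAP 6.6.

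No new assessments are needed. The cost is more than copying: 7.3.1 keeps expected complaints only as comments, so onset dates, severity, relatedness and coding may have to be completed. This applies to about 126 planned subjects (132 according to the SAP Appendix). Displayed AE counts will rise, and the flag is there to explain why. If entry is no longer feasible, the clinical study report should say that the AE tables exclude these events and name the reactions for which no arm comparison is available.

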8.2. Definition of Serious Adverse Events (SAEs)

An AE is considered "serious" if the event results in any of the following outcomes:

- death,
- a life-threatening adverse event (i.e. the subject is, in the view of the investigator, at immediate risk of death from the AE as it occurs),
- inpatient hospitalization or prolongation of existing hospitalization,
- a persistent or significant incapacity or substantial disruption of the ability to conduct normal life functions, or
- a congenital anomaly/birth defect.

Important medical events that may not result in death, but may be life-threatening, or require hospitalization may be considered serious when, based upon appropriate medical judgment, they may jeopardize the participant and may require medical or surgical intervention to prevent one of the outcomes listed in this definition. Examples of such medical events include allergic bronchospasm requiring intensive treatment in an emergency room or at home, blood dyscrasias or convulsions that do not result in inpatient hospitalization, or the development of drug dependency or drug abuse.

A suspected unexpected serious adverse reaction (SUSAR) is defined as a serious adverse reaction that is not listed in the APP13007 Investigator's Brochure or is not listed at the specificity or severity that has been observed, or that is mentioned in the APP13007 Investigator's Brochure as occurring with a class of drugs or as anticipated from the pharmacological properties of the study drug, but is not specifically mentioned as occurring with the particular drug under investigation. (See Section 8.7.2).

